- b. Harm reduction content, sent 2x/week, includes opioid overdose prevention training, instructions linking with primary care to receive opioid overdose education, naloxone, and instructions to access city-wide harm reduction sites offering sterile syringes, naloxone, and supervised injection services if desired:
- c. Motivational enhancement content, sent 3x/week, encourage uptake of OBOT services by evoking self-motivational replies and commitments to text prompts, building motivation for planned uptake, establishing a plan for uptake, adopting treatment adherence and maintenance strategies after confirming uptake per text queries, and applying coping strategies for high-risk situations that may precipitate the risk of illicit use;

- d. Medical Management content tailored to OBOT after confirming entry in treatment using 2x/week text "check-ins". Text categories will consist of: (1) Support during induction and stabilization to buprenorphine that targets buprenorphine adherence and selfmanagement with a once daily text at 9:00 am assessing for withdrawal symptoms. For a "Yes" response to withdrawal symptoms, participants will receive: (a) instructions on buprenorphine and/or comfort medication administration; (b) query for continued opioid use; and c) repeat queries at 12:00pm and 6:00pm for cravings and withdrawal symptoms. If participants report "Yes" to opioid use, they will be informed of the risk of overdose and may request a physician phone call during regular clinic hours (i.e., patient-provider communication); (2) Appointment adherence "tips" (e.g., setting written/mobile phone calendar reminders) that enhance self-management sent 1x/week; (3) Supportive content comprise alternating messages between medication adherence (e.g., buprenorphine), reinforcement of reducing harmful substance use, or 12-step meeting and counseling participation (i.e., hotlines, meeting sites / schedules, free online resources): (4) Educational content that enhance self-management with medication dosing, side-effects, overdose prevention, and online public-facing resources:
- e. Instant help allows participants to query the texting software and receive personalized motivational enhancement, educational, or clinic/social services contact details via menu items and open-ended queries captured by natural language processing to enhance patient-physician communication.

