Risks of distress associated with text messaging: This project centers on a text messaging system that supports PWUO participants to engage with opioid use disorder and social services. Although our prior feasibility studies have not yielded any adverse events related to the use of text messaging, the clinical application of any mobile health intervention comes with the attendant risks of imperfect understanding and use of this information. However, to mitigate this risk, the proposed multimodal texting intervention has undergone extensive refinement and to date, has not elicited any episodes of emotional distress. In the event PWUO participants find that the intervention is intrusive, eliciting emotional distress, or any other adverse events, they can simply reply Stop to the texting software and/or notify study staff to discontinue their continued receipt of passive reminders and informational texts. Protections against this risk are described further in 2b. In addition, during enrollment, PWUO participants in Aim 1 will be given verbal and printed instructions by the study staff to exclude the use of any identifiers during text communication, to regularly delete text messages exchanged with study staff and the HIPAA-compliant server, password protect their mobile phones and periodically change phone passwords, avoid sharing their mobile phone with friends or family, immediately report any breach of privacy committed by peers, avoid granting mobile app permissions, remain vigilant when downloading files or clicking hyperlinks from suspicious texts or emails on their phone, considering mobile phone device protection with security software that ensure personal firewalls, spam filters, anti-virus and antispyware tools, encrypt all data stored on their phone (e.g., for Android phones version 4.0 or greater, iOS running version 4.0 or higher) using federally verified encryption applications that offer a passcode to automatically encrypt all data, and avoid using open Wi-Fi.

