Patient Cohort. In this study we will use the FDA definition of serious adverse events (SAEs). Both adverse events (AEs) and SAEs will be systematically assessed at each clinic visit for the patientparticipants. We do not anticipate SAEs are AEs related to the use of text messaging which is our intervention. Any SAE, whether or not related to study intervention, will be reported to the IRB and NIDA. The initial SAE report will be followed by submission of a completed SAE report to both institutions. In the event that a patient either withdraws from the study or the investigator decides to discontinue a patient due to SAE, the patient will be monitored by the investigator via ongoing status assessment until 1) a resolution is reached, for example the problem requiring hospitalization has resolved or stabilized with no further changes expected, 2) the SAE is determined to be clearly unrelated to the study intervention, or 3) the SAE results in death. SAEs would include hospitalization (for example as the result of an opioid overdose, which is not uncommon among high-risk OUD patients) or opiate overdose resulting in death. The study team will conduct, at a minimum, an annual Data Safety Board meeting to review all SAEs. All PI's will attend this meeting. If more than 2 SAEs occur in any year, meetings of the board will be increased in frequency. All observed SAEs (again, regardless of relation to the study intervention) will be periodically reported to NIDA. A summary of the SAEs that occurred during the previous year will be included in the annual progress report to NIDA. The MPIs will be responsible for monitoring and recording both AEs and SAEs.

Provider and administrator study participants providing in-depth interview data. We do not anticipate any AEs or SAEs for the clinician and administrator participants undergoing virtual indepth interviews (Aim 2). For this sample we will also adopt the FDA definition of an SAE. AEs and SAEs for the provider and administrator sample will be handled exactly as specified for the PWUO participant cohort.

Standard AE definitions will include the following:

Adverse event: Any untoward or unfavorable medical occurrence in a human subject, including any abnormal sign (for example, abnormal physical exam or laboratory finding),

symptom, or disease temporally associated with the subject's participation in the research, whether or not considered related to the subject's participation in the research.

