Adverse events encompass both physical and psychological harms. They occur most commonly in the context of biomedical research, although on occasion, they can occur in the context of social and behavioral research. For the purposes of this study, we will not monitor known reactions to methadone or buprenorphine treatment as adverse reactions. These known reactions are specified on the FDA-approved package inserts for the medications used in this study. These include dizziness, drowsiness, withdrawal symptoms, tongue pain, nausea, vomiting, constipation, headache, insomnia, and trouble concentrating.

Serious Adverse Event: Any AE that results in any of the following outcomes:

- Death
- Life-threatening
- Event requiring inpatient hospitalization or prolongation of existing hospitalization
- Persistent or significant disability/incapacity
- Congenital anomaly/ birth defect
- Based on the appropriate medical judgement, may jeopardize the subject's health and may require medical or surgical intervention to prevent one of the other outcomes listed in this definition.

AEs are graded according to the following scale:

Mild: An experience that is transient and requires no special treatment or intervention. The experience does not generally interfere with usual daily activities. This includes transient laboratory test alterations.

Moderate: An experience that is alleviated with simple therapeutic treatments. The experience impacts usual daily activities. Includes laboratory test alterations indicating injury, but without long-term risk.

Severe: An experience that requires therapeutic intervention. The experience interrupts usual daily activities. If hospitalization (or prolongation of hospitalization) is required for treatment it becomes an SAE.

The study uses the following AE attribution scale:

Not related: The AE is clearly not related to the study procedures (i.e., another cause of the event is most plausible and/or a clinically plausible temporal sequence is inconsistent with the onset of the event).

Possibly related: An event that follows a reasonable temporal sequence from the initiation of study procedures, but that could readily have been produced by a number of other factors.

Related: The AE is clearly related to the study procedures.

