The following will be included in the DSM report: 1) brief description of protocol, 2) baseline socio-demographic characteristics, 3) retention and disposition of study participants, 4) quality assurance issues, 5) AEs, 6) SAEs, 7) efficacy, 8) suggested and actual protocol changes

Interim Data Analysis Plans

Interim analyses will be performed to evaluate safety. At each DSMB meeting, all SAEs will be evaluated and compared between study groups. If SAEs differ between groups in a manner determined to be related to study procedures, the study will be paused. Decisions to pause the study will be made by the independent DSMB.

In addition to consistent monitoring by members of the research team for adverse events, quarterly interim analyses of the survey data, quality control checks, and study activities will also be performed to ensure that all participant data are protected and there are no adverse events or harm to participants. During this review, validity and integrity of the data will also be monitored.

References

- [name] JD, Nunes Jr EV, Novo P, et al. Comparative effectiveness of extended-release naltrexone versus buprenorphine-naloxone for opioid relapse prevention (X: BOT): a multicentre, open-label, randomised controlled trial. *Lancet*. 2018;391(10118):309-318.

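### Non-serious labelled buprenorphine reactions that follow a study message cannot be recorded as AEs, so a finding of no text-related AEs would be partly true by definition

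*Combined protocol and SAP*

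**What the plan says.** Collection and Reporting of SAEs and AEs begins with a broad AE definition: any unfavourable medical occurrence associated in time with participation, related or not. It then narrows the scope: "For the purposes of this study, we will not monitor known reactions to methadone or buprenorphine treatment as adverse reactions". The excluded reactions are those on the package inserts, with examples: "These include dizziness, drowsiness, withdrawal symptoms, tongue pain, nausea, vomiting, constipation, headache, insomnia, and trouble concentrating". Nothing is said about reactions that follow a study message. The same section gives a three-level scale for relatedness to study procedures, defines "Serious Adverse Event: Any AE that results in any of the following outcomes", and states the expectation that "We do not anticipate SAEs are AEs related to the use of text messaging which is our intervention".

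Under Study Procedures: Patients, the medical management texts go to arms 1 and 2 once treatment entry is confirmed. During induction and stabilization they include "a once daily text at 9:00 am assessing for withdrawal symptoms". A *Yes* reply brings "a) instructions on buprenorphine and/or comfort medication administration; (b) query for continued opioid use", with repeat queries at midday and in the evening. Table 1 also has a sample message about the time of day to take the dose.

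Potential risks to participants accepts that clinical use of any mobile health tool "comes with the attendant risks of imperfect understanding and use of this information". The one between-arm safety comparison is in Interim Data Analysis Plans: "At each DSMB meeting, all SAEs will be evaluated and compared between study groups".

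**The concern.** Leaving labelled drug reactions out of AE reporting is reasonable when the drug is background care prescribed by others. Here the randomized component itself comments on how to take that drug, and it does so in response to a symptom on the exclusion list. A participant who misreads such a message and then has more withdrawal, vomiting or drowsiness is a plausible case of the risk the protocol names. The exclusion removes that case before anyone can rate it as possibly related or related.

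At stake is the trial's safety statement. The plan expects no text-related AEs. For non-serious labelled reactions, the recording rule produces that result whatever happens. The DSM report could then describe the messages as free of related AEs on a count that was closed to the most relevant events.

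**Working it through.** **What each safety channel records for a labelled reaction after a study message**

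| Channel (section) | Non-serious | Serious |
|---|---|---|
| AE record and relatedness scale (Collection and Reporting of SAEs and AEs) | Excluded | Excluded as an AE, but see next row |
| SAE reporting (same section) | Not applicable | Any SAE is reported regardless of relation; hospitalization makes an event an SAE |
| Between-arm comparison (Interim Data Analysis Plans) | None stated | All SAEs compared by arm |
| Social harm form (Safety Monitoring Plan) | Asks about problems from texts and has a physical category, but is framed around non-medical experiences and is in neither list of DSM report contents | Same |
| Text-log measures (Data Safety and Quality Assurance) | Messages sent and response rates; withdrawal replies exist only in the texting arms | Same |

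The gap is therefore in the non-serious column. One ambiguity remains in the serious column: an SAE is defined as a type of AE, and the definition comes after a sentence that removes these reactions from AE monitoring. Read with the rest of the section, capture as an SAE is the natural interpretation.

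**Size, as a range**

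The plan gives no reaction rate and proposes no bound, so what follows is a yardstick only. The Cohort section gives two planning inputs, about 5% uptake of medication and about 25% referral completion. There are 84 participants per arm, so 168 are texted.

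*Using 25% / 35% / 45%, with referral completion taken as a buprenorphine start (assumed):*
- Starters: 84 × 0.25 = 21.0; 84 × 0.35 = 29.4; 84 × 0.45 = 37.8.
- Texted starters: 29.4 + 37.8 = 67.2.

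*Using 5% in control, with the plan's odds ratios of 1.5 and 2.0 applied to uptake (assumed):*
- Control odds: 0.05/0.95 = 0.0526.
- Arm 2: odds 0.0789, probability 0.0732, starters 84 × 0.0732 = 6.1.
- Arm 1: odds 0.1053, probability 0.0952, starters 84 × 0.0952 = 8.0.
- Control starters: 84 × 0.05 = 4.2. Texted starters: 14.1.

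*What a zero count would seem to show:* the one-sided 95% upper bound for zero events in 168 is 1 − 0.05^(1/168) = 1.77%, or 0.0177 × 168 = 2.97 people.

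*Share of texted starters with a text-caused excluded reaction at which that bound is wrong:*
- 25% input: 2.97/67.2 = 4.4%.
- 5% input: 2.97/14.1 = 21%.

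The threshold moves almost fivefold with the choice of input, so no single figure should be quoted.

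**The case against.** A reader might infer that harm from text-guided medication use cannot appear in the safety data at all. The documents do not support that. Every SAE is reported whatever its relation, hospitalization makes an event serious, and all SAEs are compared by arm. Only labelled reactions are excluded, so an unlabelled one would still be an AE.

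A reader might also infer that software is changing the doses of people without clinical oversight. The documents do not support that either. The content follows confirmed treatment entry, is based on federal and consensus guidelines, and comes with the option of a physician call if opioid use is reported. The instructions sent after a *Yes* are not reproduced, so a dose change is conjecture. The lettering of the replies also does not establish that the instructions precede the query about opioid use.

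The strongest counterargument is that counting labelled reactions by arm would mislead. If texting raises uptake, the texting arms will have more drug reactions even if no message causes any. This stands, and it rules out recording every labelled reaction and testing the arms against each other. It does not answer the narrower point about reactions that someone attributes to a study message.

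Other oversight exists: monthly review of reports of adverse consequences, quarterly checks of survey data, and the social harm question. These narrow the gap but do not return such events to the AE count or to the relatedness scale.

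**Conclusion.** The point holds for non-serious labelled reactions that follow a study text or PRC message. As written, they cannot be recorded as AEs or rated for relatedness, so a statement of no text-related AEs would be partly true by definition. This follows from the text and needs no assumed rate.

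The size is uncertain. On the plan's two inputs, the break-even share is 4.4% to 21% of texted starters, subject to the assumptions shown above. Actual uptake may differ from both inputs, since eligibility requires interest in starting buprenorphine.

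The point does not extend to serious reactions, where only a clarifying clause is needed, or to the primary outcome, sample size or efficacy inference. It is a gap in safety ascertainment that is cheap to close.

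**What to change.** In Collection and Reporting of SAEs and AEs, amend the exclusion along these lines: known reactions to methadone or buprenorphine are not recorded as AEs if they are non-serious and neither the participant nor staff attribute them to a study text or PRC message; attributed reactions are recorded as AEs and rated on the existing relatedness scale; any reaction meeting a serious criterion is an SAE.

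Add one item to the AE form at the 3-, 6- and 12-month visits, worded identically in all arms. It should ask whether such a reaction occurred and whose advice on taking the medication was being followed (study text, PRC, clinic, other). List the attributed reactions under the existing AE item of the DSM report.

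The cost is a short wording change and one question at visits already planned. The drawbacks are that attribution by recall over several months is noisy, and that raw arm counts also reflect higher buprenorphine uptake. The counts should be reported descriptively, without a between-arm test. Withdrawal replies from the text logs should be kept separate because the control arm has none.

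### The exclusion of known methadone and buprenorphine reactions from adverse-event monitoring has no severity limit, contradicts the AE definition, leaves serious cases unclear and is likely to fall unequally on the arms

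*Combined protocol and SAP*

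**What the plan says.** Under Collection and Reporting of SAEs and AEs, the standard definitions count any unfavourable medical event or symptom during participation as an AE, "whether or not considered related to the subject's participation in the research". The same definition then adds that "we will not monitor known reactions to methadone or buprenorphine treatment as adverse reactions", with examples: "These include dizziness, drowsiness, withdrawal symptoms, tongue pain, nausea, vomiting, constipation, headache, insomnia, and trouble concentrating". No severity limit is given. The text refers to the two drugs as medicines that the study uses, although the section names text messaging as the intervention.

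An SAE is defined as an AE with one of several outcomes, hospitalization among them. The Patient Cohort paragraph requires every SAE to be reported regardless of relatedness and gives hospitalization as an example. The severity scale says that an event needing hospitalization becomes an SAE. Reportable SAEs go to the IRB within 24 hours. Under Interim Data Analysis Plans, "At each DSMB meeting, all SAEs will be evaluated and compared between study groups", and a difference judged related to study procedures pauses the study.

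Under Study Procedures: Patients, the Medical Management text content starts once treatment entry is confirmed. In arms 1 and 2 it supports induction "with a once daily text at 9:00 am assessing for withdrawal symptoms", and a positive reply brings "instructions on buprenorphine and/or comfort medication administration". The control arm receives no texts. The paragraph on distress from text messaging concedes that "the clinical application of any mobile health intervention comes with the attendant risks of imperfect understanding and use of this information".

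**The concern.** There are two separate problems.

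First, the definitions do not agree. A symptom that counts as an AE whatever its cause is then removed because of its cause. Staff must attribute it to medication before deciding whether to log it, so the relatedness scale is never applied. Since the SAE definition rests on the AE definition, two sites could classify the same hospitalization for withdrawal or sedation differently. That classification decides whether expedited reporting applies and whether the event enters the comparison on which pausing depends.

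Second, the exclusion is not neutral between arms. It applies to people on methadone or buprenorphine, and the intervention is meant to put more people on buprenorphine. If it works, the texting arms lose more of these symptoms from their AE records than TAU does. AEs are a listed item of the DSM report, so a reader of that report could see a lower AE burden in the texting arms that comes from the recording rule.

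**Working it through.** **Consistency of the definitions.** Take a participant on buprenorphine who is hospitalized for withdrawal.
- By the general AE definition: an AE, and with hospitalization an SAE.
- By the exclusion, read literally: not monitored as an adverse reaction. If therefore not an AE, it is not an SAE, because an SAE must first be an AE.
- By the Patient Cohort paragraph and the severity scale: hospitalization points to an SAE, to be reported whatever its cause.

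The exclusion speaks of reactions rather than events, but it sits inside the AE definition, so the wording does not settle the matter. Nothing says which statement prevails.

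**Who is affected.** The plan gives no reaction rate and no figure for treatment starts by arm. As a stand-in I use the referral-completion rates in the Cohort section (25%, 35%, 45%) and 84 per arm. With p the proportion starting treatment, starters = 84 × p. Those for whom the same symptoms clearly remain recordable = 84 × (1 − p).

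| | TAU | Texting only | Texting + peer coach |
|---|---|---|---|
| p | 0.25 | 0.35 | 0.45 |
| Starters | 21.0 | 29.4 | 37.8 |
| Others | 63.0 | 54.6 | 46.2 |
| Recorded symptoms relative to TAU, (1 − p)/0.75 | 1 | 0.65/0.75 = 0.87 | 0.55/0.75 = 0.73 |

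The last row assumes the same symptom risk for non-starters in every arm, and that starters are covered by the exclusion for all of follow-up. Recorded symptoms would then be about 13% and 27% lower than in TAU. Starts occur during follow-up and some people stop, so the real gap would be smaller.

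**Range for uptake.** The Cohort section also cites about 5% for MOUD uptake. Applying its odds ratios of 1.5 and 2.0 to that base:
- Odds in TAU: 0.05/0.95 = 0.0526.
- Texting only: 0.0526 × 1.5 = 0.0789, so p = 0.0789/1.0789 = 0.073.
- Texting + peer coach: 0.0526 × 2.0 = 0.1053, so p = 0.1053/1.1053 = 0.095.
- Recorded relative to TAU: 0.927/0.95 = 0.98 and 0.905/0.95 = 0.95.

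The gap for texting plus peer coach thus runs from about 5% to 27%, depending on uptake.

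**How much of the gap would be false.** Let r be the symptom risk of starters relative to non-starters (not in the documents). On the first set of rates, the true ratio of texting plus peer coach to TAU is (0.55 + 0.45r)/(0.75 + 0.25r), while the recorded ratio stays at 0.73.
- r = 0: 0.55/0.75 = 0.73. The record is right.
- r = 1: 1.00/1.00 = 1.00. The record shows 27% fewer where there is no difference.
- r = 2: 1.45/1.25 = 1.16. The record shows fewer where there are more.

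**Other sources.** Text replies on withdrawal exist only in arms 1 and 2. The process measures listed under Data Safety and Quality Assurance are messages sent and percent answered, not symptom content. Table 2 surveys sleep and cognition in all arms, which overlaps with two listed reactions, but it has no withdrawal scale and these items are not AE records.

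**The case against.** A reader might infer that the exclusion keeps the intervention's most plausible harm out of the between-arm safety comparison altogether. The documents do not support that. The only comparison specified is of SAEs, so non-serious withdrawal or drowsiness would be absent from it even if the exclusion were deleted. For serious cases, the Patient Cohort paragraph and the severity scale both point towards inclusion; the status is contradictory, and loss is not certain. Nor do the documents rank medication reactions as the most plausible harm. They name loss of confidentiality, distress and social harm, and give overdose as an SAE example. The sentence on imperfect use of texted information stands under distress and does not mention medication reactions.

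A reader might also take the 67 or so expected starters in the two texting arms (29.4 + 37.8 = 67.2) as a measure of harm. They are possible starters only. The medication texts reach only people with confirmed treatment entry, and withdrawal in someone on neither drug is not clearly excluded.

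The social-harm question in the Safety Monitoring Plan is a real safeguard. It asks at scheduled visits about problems caused by enrolment or by study texts, covers physical harm, and brings events to the principal investigators within 24 hours. But it records only what participants themselves attribute to the study, so it does not replace unattributed AE recording.

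Finally, leaving out expected, non-serious reactions to treatment prescribed outside the intervention is a disclosed choice and does not affect the primary outcome. That is fair. It does not justify an exclusion without a severity limit. The further objection that better linkage would itself raise crude counts of these reactions also stands, and the fix has to allow for it.

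**Conclusion.** The point holds as an inconsistency with a likely recording imbalance. The contradiction over serious cases rests on the text alone and needs no assumption. It should be resolved because expedited reporting and the pausing rule depend on it. The imbalance follows from the design in direction: the more the intervention raises treatment starts, the more symptoms the rule removes from the texting arms. Its size is illustrative. It rests on referral completion standing in for treatment starts, equal symptom risk among non-starters, and an exclusion lasting throughout follow-up. How misleading it would be depends on a relative risk that the documents do not give. No comparable between-arm data on these reactions are planned in the safety reporting. Nothing here shows that the texts cause harm.

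**What to change.** - Reconcile the AE definition, the exclusion and the Patient Cohort paragraph. State that any known medication reaction meeting a seriousness criterion is an SAE, is reported as one, and enters the comparison under Interim Data Analysis Plans.
- Record non-serious reactions the same way in all three arms, at the existing visits, with the existing severity and relatedness scales.
- Tabulate them by arm, both overall and among participants who started treatment, so that more starts are not read as harm. The second table is descriptive, because starting treatment happens after randomization.
- Do not set withdrawal replies from the texting software against TAU, which has no such log.
- Correct the wording that presents methadone and buprenorphine as medicines that the study uses.
- Use the existing social-harm question to capture attribution to study texts; a new CRF item is optional.

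The cost is protocol wording, one or two safety tables and more non-serious AE records. AEs are already elicited at study visits. The change concerns the recording and classification of events only; no clinical rule is proposed.
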